6.3.2. Dose Delay for Cetrelimab

CCI

The criteria for discontinuation of study treatment are described in Section 6.3.3 and Section 10.2.

6.3.3. Cetrelimab Associated Toxicities Leading to Discontinuation of Study Treatment

A subject must discontinue cetrelimab if:

- The investigator believes that for treatment-emergent toxicity it is in the best interest of the subject to discontinue study treatment
- Grade 4 toxicities except for endocrinopathies that are controlled with replacement hormones
- Grade 2 or 3 immune-related AEs (irAEs) that persist despite treatment modifications or corticosteroid dosing cannot be reduced to ≤ 10 mg prednisone or equivalent per day within 12 weeks

- A treatment-related AE does not resolve to Grade ≤ 1 within 12 weeks of the last dose of study drug unless otherwise agreed to by the sponsor medical monitor and the investigator based on evidence of clinical benefit
- Any non-hematological treatment-related event occurs a second time at Grade ≥ 3 severity
- Grade ≥ 3 (or recurrent Grade 2) pneumonitis
- Grade ≥ 3 nephritis with creatinine ≥ 3 xULN
- Grade ≥ 3 elevation of AST or ALT > 5 xULN or total bilirubin > 3 xULN
- For subjects with baseline Grade 2 elevation of AST or ALT due to liver metastasis, only Grade ≥ 3 elevations that are $\geq 50\%$ of baseline for ≥ 7 days will require discontinuation of study treatment
- Liver metastasis with baseline Grade 2 elevation of AST or ALT, hepatitis with AST or ALT increase $\geq 50\%$ and lasts ≥ 1 week
- Grade ≥ 3 IRRs
- Immune-mediated encephalitis.

If a subject's cetrelimab is discontinued, this will not result in automatic withdrawal of the subject from the study. The subject may continue on the other study treatments(s). Following cetrelimab discontinuation, the subject should complete the End-of-Treatment Visit as described in Time and Events Schedule and Section 9.1.3. Once a subject discontinues treatment, the subject may not be retreated with the study drug.

Following Amendment 5 and after end of study data collection timepoint has been achieved, the eCRF will be closed and only SAEs must be reported through the company safety repository.

6.3.4. Guidelines for Management of Immune-Related Adverse Events and Adverse Events of Clinical Interest

Therapy with immuno-oncology agents such as cetrelimab can lead to specific irAEs that differ in nature, severity and duration as compared to AEs caused by agents with a different mode of action. Early recognition and management of these irAEs may mitigate more severe/subsequent toxicity. However, differential diagnoses including non-inflammatory etiologies as well as the impact of the underlying malignant disease and/or concomitant medication should be evaluated according to standard medical practice.

Management algorithms have been developed to assist investigators in assessing and managing specific irAEs following administration of nivolumab ([Knowles 2015](#)); ([Nivolumab 2016](#)) and pembrolizumab ([Keytruda® 2014](#)); ([Oken 1982](#)). These guidelines are presented below and should be followed for cetrelimab. In addition to the management algorithms provided in following sections, it is recommended that irAEs are managed according to the general treatment guidelines outlined for ipilimumab ([Ipilimumab 2015](#)). These guidelines recommend the following:

1. Subjects should be evaluated to identify any alternative etiology.
2. In the absence of a clear alternative etiology, all events of an inflammatory nature should be considered immune-related.

3. Symptomatic and topical therapy should be considered for low-Grade events.
4. Systemic corticosteroids should be considered for a persistent low-Grade event or for a severe event.
5. More potent immunosuppressants should be considered for events not responding to systemic corticosteroids (eg, anti-tumor necrosis factor agents or mycophenolate).

If delaying the dose is necessary to ameliorate a toxicity, follow the guidance in Section [6.3.2](#).

6.3.4.1. Gastrointestinal Adverse Events

Diarrhea and colitis have been observed in subjects receiving anti-PD-1 therapies. Early recognition and treatment of diarrhea and colitis are critical to their management (see [Table 16](#)). Subjects should be advised to seek immediate medical evaluation if they develop new-onset diarrhea, blood in stool, or severe abdominal pain or if they have worsening of baseline diarrhea. In subjects with pre-existing diverticulosis and/or diverticulitis receiving concomitant medication with corticosteroids, nonsteroidal anti-inflammatory drugs, and opioid analgesics together with anti-PD-1 therapies, diverticular perforation has been observed.

Table 16: Management of Immune-Related Gastrointestinal Adverse Events

For guidelines for delaying a dose, refer to Section 6.3.2.	
Grade 1	Symptomatic treatment according to institutional standards Close monitoring; instruct subject to report worsening immediately and treat as Grade ≥2
Grade 2	≤5 days: Symptomatic treatment according to institutional standards >5 days or recurrence: 0.5–1.0 mg/kg/d methylprednisolone; consider prophylactic antibiotics; Persistence or worsening despite steroids >3 days: treat as Grade 3/4 Improvement to ≤Grade 1: taper steroids over at least 4 weeks, consider prophylactic antibiotics for opportunistic infections, resume study therapy per protocol
Grade 3–4	Immediately: 1.0–2.0 mg/kg/d methylprednisolone IV; consider prophylactic antibiotics and lower endoscopy Persistence >3 days or recurrence: add infliximab 5 mg/kg (if no contraindication such as perforation or sepsis) Improvement to ≤Grade 2 within ≤3 days: taper steroids over at least 4 weeks
General	The oral corticosteroid equivalent of the recommended IV dose may be considered for ambulatory subjects; the lower bioavailability of oral corticosteroids needs to be considered. Clinical caution should be exercised, for subjects receiving concomitant medications of corticosteroids, nonsteroidal anti-inflammatory drugs, or opioid analgesics. In addition, monitor for signs and symptoms of potential perforation, especially in subjects with known diverticular disease. Narcotics should be used with caution as pain medicines may mask the signs of colonic perforation.

6.3.4.2. Hepatic Adverse Events

Hepatic AEs, including elevated liver function tests (LFTs) and, infrequently, drug induced liver-injuries (DILI) have been observed following treatment with anti-PD-1 therapies. Early recognition and treatment of elevated LFTs and DILI are critical to their management (see [Table 17](#)). Subjects should be advised to seek medical evaluation if they notice jaundice (yellow appearance of skin or sclera) or if they develop bruising, bleeding, or right-sided abdominal pain. Physicians should monitor LFTs prior to anti-PD-1 therapies.

Subjects who have a predominant cholestatic pattern of liver injury (dominant increase in ALP relative to ALT /AST) should be further evaluated to exclude a diagnosis of treatment emergent sclerosing cholangitis. An evaluation may include ultrasound of liver, cholangiography and referral to gastroenterologist and/or a hepatologist.

Table 17: Management of Immune-Related Hepatic Adverse Events

For guidelines for delaying a dose, refer to Section 6.3.2.	
Grade 1	Monitor LFTs as outlined in the protocol; Worsening: treat as Grade ≥ 2
Grade 2	Monitor every 3 days; Returning to baseline: resume per protocol monitoring LFT elevation >5 days or worsening: 0.5-1.0 mg/kg/d methylprednisolone IV or oral equivalent; consider prophylactic antibiotics LFT return to \leqGrade 1 or baseline: taper steroids over at least 4 weeks; resume routine monitoring and resume study treatment per protocol
Grade 3-4	Monitor every \leq 2 days; Immediately: 1.0-2.0 mg/kg/d methylprednisolone IV or IV equivalent; start prophylactic antibiotics; consult gastroenterologist Persistence >3 days or recurrence: add mycophenolate mofetil 1g BID; if no response within \leq 5 days consider other immunosuppressants per local guidelines LFT return to Grade 2: stop immunosuppressants LFT return to \leqGrade 1: taper steroids over at least 4 weeks

Abbreviations: BID = twice daily; LFT = liver function test

6.3.4.3. Endocrinopathies

Endocrinopathies have been observed following treatment with anti-PD-1 therapies. The events have typically been identified through either routine periodic monitoring of specific laboratory tests (eg, Thyroid Stimulating Hormone [TSH]) or as part of a work-up for associated symptoms (eg, fatigue). Events may occur within weeks of beginning treatment, but also have been noted to occur after many months (while still on treatment). More than 1 endocrine organ may be involved (eg, hypophysitis [pituitary inflammation] may need to be evaluated at the time adrenal insufficiency or thyroid disorder is suspected). Subjects should be advised to seek medical evaluation if they notice new-onset fatigue, lightheadedness, or difficulty with vision or if baseline fatigue worsens. See [Table 18](#) for management guidelines.

Table 18: Management of Immune-Related Endocrinopathies

For guidelines for delaying a dose, refer to Section 6.3.2.	
Asymptomatic TSH elevation	TSH <0.5 xULN or TSH >2 xULN or TSH >ULN in 2 subsequent measurements: include free T4 assessment prior/after subsequent cycles of study treatment; consider endocrinology consultation
Symptomatic endocrinopathy	Assess endocrine function with appropriate laboratory testing; consider pituitary MRI scan. With abnormal lab and pituitary scan: 1.0–2.0 mg/kg/d methylprednisolone IV or oral equivalent; initiate appropriate hormone therapy; consider prophylactic antibiotics 
 In hyperthyroidism, non-selective beta-blockers (eg, propranolol) are suggested as initial therapy. In hypothyroidism, thyroid hormone replacement therapy, with levothyroxine or liothyronine, is indicated per standard of care.

For guidelines for delaying a dose, refer to Section 6.3.2.	
	Clinical and laboratory improvement: taper steroids over at least 4 weeks; subjects with adrenal insufficiency may need to continue steroids with mineralocorticoid component Without abnormal lab and pituitary scan but symptoms persist: repeat laboratory assessments in ≤ 3 weeks and MRI in 4 weeks
Suspicion of adrenal crisis (eg, severe dehydration, hypotension, shock out of proportion to current illness)	Rule out sepsis Immediately: initiate/stress dose of IV steroids with mineralocorticoid activity; fluids IV; consult endocrinologist Adrenal crisis ruled out: treat as symptomatic endocrinopathy
Type 1 diabetes mellitus (if new-onset, including diabetic ketoacidosis [DKA]) or \geq Grade 3 Hyperglycemia, if associated with ketosis (ketonuria) or metabolic acidosis (DKA)	For T1DM or Grade 3-4 Hyperglycemia: Insulin replacement therapy is recommended for Type 1 diabetes mellitus and for Grade 3-4 hyperglycemia associated with metabolic acidosis or ketonuria. Evaluate subjects with serum glucose and a metabolic panel, urine ketones, glycosylated hemoglobin, and C-peptide.
General	Subjects on IV steroids may be switched to an equivalent dose of oral corticosteroids (eg, prednisone) at start of tapering or earlier, once sustained clinical improvement is observed. The lower bioavailability of oral corticosteroids needs to be considered.

Abbreviations: LLN = lower limit of normal; MRI = magnetic resonance imaging; T1DM = Type 1 diabetes mellitus; ULN = upper limit of normal

6.3.4.4. Rash

Rash and pruritus were the most common skin irAEs observed following treatment with anti-PD-1 therapies. The rash was typically focal with a maculopapular appearance occurring on the trunk, back, or extremities. Most cases have been of low or moderate Grade. In some cases, rash and pruritus resolved without intervention. Subjects should be advised to seek medical evaluation if they notice new-onset rash. Early consultation with a dermatology specialist and a biopsy should be considered if there is uncertainty as to the cause of the rash, or if there is any unusual appearance or clinical feature associated with it. A case of toxic epidermal necrolysis occurred in a subject receiving concomitant prophylaxis with trimethoprim/sulfamethoxazole, and it is possible that the initial rash was due to a sulfa-hypersensitivity reaction that was eventually augmented by anti-PD-1 therapies. This case highlights the possible importance of discontinuing other suspected drugs in the management of rash. See [Table 19](#) for management guidelines.

Table 19: Management of Rash

For guidelines for delaying a dose, refer to Section 6.3.2.	
Grade 1-2	Immediately: Symptomatic therapy (eg, antihistamines, topical steroids) Persistence ≤ 2 weeks or recurrence: consider skin biopsy; consider 0.5-1.0 mg/kg/d methylprednisolone IV or oral equivalent; consider prophylactic antibiotics Improvement to Grade ≤ 1: taper steroids over at least 4 weeks Worsening to Grade > 2: treat as Grade 3-4
Grade 3-4	Immediately: consult dermatologist; consider skin biopsy; start 1.0-2.0 mg/kg/d methylprednisolone IV or IV equivalent; add prophylactic antibiotics Improvement to \leq Grade 1: taper steroids over at least 4 weeks
General	Subjects on IV steroids may be switched to an equivalent dose of oral corticosteroids (eg, prednisone) at start of tapering or earlier, once sustained clinical improvement is observed. The lower bioavailability of oral corticosteroids needs to be considered.

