6.3.4.5. Renal Adverse Events

Elevated creatinine and biopsy-confirmed tubulointerstitial nephritis and allergic nephritis have been infrequently observed following treatment with anti-PD-1 therapies. Physicians should monitor creatinine regularly (see [Table 20](#)).

Table 20: Management of Renal Adverse Events

For guidelines for delaying a dose, refer to Section 6.3.2 .	
Grade 1	Monitor creatinine weekly Creatinine returns to baseline: continue monitoring per protocol Creatinine increases: treat as Grade ≥ 2
Grade 2-3	Monitor creatinine every ≤ 3 days Immediately: start 0.5-1.0 mg/kg/d methylprednisolone IV or oral equivalent; consider prophylactic antibiotics; consider renal biopsy Improvement to Grade ≤ 1: taper steroids over at least 4 weeks Persistence >7 days or worsening: treat as Grade 4
Grade 4	Monitor creatinine daily Immediately: consult nephrologist; consider renal biopsy; start 1.0-2.0 mg/kg/d methylprednisolone IV or IV equivalent; add prophylactic antibiotics Improvement to Grade ≤ 1: taper steroids over at least 4 weeks
General	Subjects on IV steroids may be switched to an equivalent dose of oral corticosteroids (eg, prednisone) at start of tapering or earlier, once sustained clinical improvement is observed. The lower bioavailability of oral corticosteroids needs to be considered.

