6.3.4.7. Pulmonary Adverse Events

Pulmonary AEs including radiographic changes (eg, focal ground glass opacities and patchy infiltrates) indicative of drug-related pneumonitis have been observed in subjects receiving anti-PD-1 therapies. These pulmonary AEs were either asymptomatic or associated with symptoms such as dyspnea, cough, or fever. The initial occurrence of pulmonary AEs may be as early as after a single dose of anti-PD-1 therapies or delayed after prolonged therapy. Early recognition and treatment of pneumonitis is critical to its management (see [Table 22](#)). Subjects should be advised to seek medical evaluation promptly if they develop new-onset dyspnea, cough, or fever or if they have worsening of these baseline symptoms.

Table 22: Management of Pulmonary Adverse Events

For guidelines for delaying a dose, refer to Section 6.3.2 .	
Grade 1	Monitor for symptoms every 2-3 days; consider pulmonary and infectious-disease consult; re-image every 3 weeks Worsening: treat as \geq Grade 2
Grade 2	Monitor symptoms daily; re-image every 1-3 days; pulmonary and infectious-disease consultation; consider bronchoscopy and lung biopsy; consider hospitalization Immediately: start 1.0 mg/kg/d methylprednisolone IV or oral equivalent; prophylactic antibiotics Persistence for 2 weeks or worsening: treat as Grade 3-4 Improvement to \leq Grade 1 or baseline: taper steroids over at least 4 weeks
Grade 3-4	Hospitalize; pulmonary and infectious-disease consult; consider bronchoscopy and lung biopsy Immediately: 2-4 mg/kg/d methylprednisolone or IV equivalent; add prophylactic antibiotics; Persistence for 2 days or worsening: add immunosuppression (eg, infliximab, cyclophosphamide, IVIG, or mycophenolate mofetil) Improvement to \leq Grade 2: taper steroids over at least 6 weeks
General	Subjects on IV steroids may be switched to an equivalent dose of oral corticosteroids (eg, prednisone) at start of tapering or earlier, once sustained clinical improvement is observed. The lower bioavailability of oral corticosteroids needs to be considered.

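### Table 19 reverses the duration trigger for Grade 1-2 rash: biopsy and systemic steroids are tied to persistence of 2 weeks or less instead of more than 2 weeks

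*Protocol*

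**What the plan says.** Section 6.3.4 of the Protocol tells investigators to follow its immune-related adverse event algorithms for cetrelimab. Two of its general rules apply to mild events. The third reads "Symptomatic and topical therapy should be considered for low-Grade events" and the fourth "Systemic corticosteroids should be considered for a persistent low-Grade event or for a severe event".

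Table 19 (Section 6.3.4.4) applies this to rash. The Grade 1-2 row has four lines:

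1. Symptomatic therapy at once, such as antihistamines or topical steroids.
2. "Persistence ≤ 2 weeks or recurrence: consider skin biopsy", followed on the same line by considering methylprednisolone 0.5-1.0 mg/kg/d and prophylactic antibiotics.
3. On improvement to Grade 1 or lower, a steroid taper over at least 4 weeks.
4. On worsening above Grade 2, management as Grade 3-4.

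The text above the table describes rash and pruritus as the commonest skin immune-related events with anti-PD-1 therapy, mostly low or moderate in grade, and adds: "In some cases, rash and pruritus resolved without intervention".

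**The concern.** The inequality on the second line points the wrong way for an escalation step. Persistence and recurrence are both reasons to do more after first-line care has failed, and an upper time limit does not fit that purpose.

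Read literally, the line has two faults. A site may consider biopsy and systemic steroids for a mild rash that has only just appeared and might resolve untreated. And a rash that drags on past 2 weeks, the case for which escalation is meant, finds no step in the row unless it recurs or worsens.

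What is at stake is subject management. Steroids begun under this row carry a taper of at least 4 weeks. Failure to bring the dose down to 10 mg prednisone or less per day within 12 weeks forms part of a cetrelimab discontinuation criterion for Grade 2 or 3 immune-related events (Section 6.3.3). Table 15 permits cetrelimab retreatment with rash up to Grade 2, so the affected subjects may stay on drug. Nothing in the estimation of response rate or in the safety summaries depends on the line.

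**Working it through.** The plan states no figure to reproduce and no power or error-rate calculation applies. The check is whether the row works as a sequence and whether its direction agrees with the rest of the protocol.

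**Step 1: run the row both ways.**

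| Course of a Grade 1-2 rash | As printed (≤ 2 weeks) | With the sign turned (> 2 weeks) |
|---|---|---|
| Day 1, new | Symptomatic therapy and the step-up both apply | Symptomatic therapy only |
| Beyond 2 weeks, no recurrence, no worsening | No step applies | Step-up applies |
| Recurs | Step-up applies | Step-up applies |
| Worsens above Grade 2 | Treat as Grade 3-4 | Treat as Grade 3-4 |

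Only the right-hand column gives an orderly sequence.

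**Step 2: compare with the general rules.** Rules 3 and 4 of Section 6.3.4 put symptomatic and topical care first for low-grade events and reserve systemic steroids for events that are persistent or severe. The printed line brings steroids in before any persistence and leaves them out after it.

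**Step 3: compare with the closest parallel.** Table 16, Grade 2 (Section 6.3.4.1) prints both branches. An event of 5 days or less gets symptomatic treatment only. The longer branch reads ">5 days or recurrence: 0.5–1.0 mg/kg/d methylprednisolone". The dose tier is the same and recurrence is the same alternative trigger. Table 19 attaches the steroid to the side of the cut-off that Table 16 gives to symptomatic care.

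**Step 4: count the persistence steps that state a duration in the sibling tables.**

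| Table | Steps with a duration | Number | Minimums |
|---|---|---|---|
| 16 Gastrointestinal | > 5 days; > 3 days despite steroids; > 3 days | 3 | 3 |
| 17 Hepatic | > 5 days; > 3 days | 2 | 2 |
| 20 Renal | > 7 days | 1 | 1 |
| 22 Pulmonary | 2 weeks; 2 days | 2 | 2 |
| **Total** | | **3 + 2 + 1 + 2 = 8** | **8** |
| 19 Rash | ≤ 2 weeks | 1 | 0 |

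Three of the eight read "LFT elevation >5 days or worsening: 0.5-1.0 mg/kg/d methylprednisolone IV or oral equivalent" (Table 17), "Persistence >7 days or worsening: treat as Grade 4" (Table 20) and "Persistence for 2 weeks or worsening: treat as Grade 3-4" (Table 22). Tables 18 and 23 mention persistence without a duration and are left out. The wait of up to 5 days for a response to mycophenolate in Table 17 concerns non-response to treatment and is not counted.

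**Step 5: look at every row using the 0.5-1.0 mg/kg/d tier.** There are five. Table 16 Grade 2 and Table 17 Grade 2 require more than 5 days. Table 20 Grade 2-3 starts the tier, and Table 21 Grade 2 considers it, under the heading that marks immediate action. Table 19 is the fifth. Its steroid sits on a separate line after the immediate one, so by the protocol's own layout it is meant to come later.

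**Step 6: check the other 2-week cut-offs.** In the erdafitinib guidance for oral mucositis and nail changes (Tables 10 and 12), Grade 2 events that resolve within 2 weeks on first occurrence restart at the same dose, while those taking more than 2 weeks restart one level lower. The stronger action again falls on the longer duration.

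**The case against.** The best case for leaving the line alone has five parts.

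- **It rests on one symbol.** The same section states the rash threshold nowhere else, so a typesetting or file-conversion fault cannot be wholly excluded. However, the other two inequalities in the same row, for improvement and for worsening, read correctly. This calls for a look at the page and at the source algorithm; it does not make the printed line right.
- **Early steroids are not foreign to the protocol.** Two of the five rows at this dose tier, in Tables 20 and 21, act at once. That is a fair limit on the comparison in Table 17 and elsewhere, and it is why all five rows are listed above. But those rows say so by labelling the action as immediate, and Table 19 does not.
- **Early biopsy is partly endorsed.** The text above Table 19 advises early dermatology consultation and considering biopsy when the cause is uncertain or the appearance unusual. This stands for such cases. It does not support biopsy as a duration-based step for every mild rash.
- **The gap beyond 2 weeks has backstops.** Rule 4 of Section 6.3.4 allows steroids for any persistent low-grade event, and Section 6.3.3 requires stopping cetrelimab for Grade 2 or 3 immune-related events that persist despite treatment modification. This also stands: an investigator who reads beyond the table is not left without guidance.
- **The consequence is small.** Each action on the line is only to be considered, and an experienced oncologist would probably read the line as intended. That bears on the weight of the point. It does not explain why a safety table should carry a threshold the reader must mentally invert.

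**Conclusion.** The point holds. The Grade 1-2 step-up in Table 19 is printed with its inequality reversed. It conflicts with the row's own symptomatic-first line, with rules 3 and 4 of Section 6.3.4, with the split in Table 16 at the same dose, and with all 8 duration-based persistence steps in Tables 16, 17, 20 and 22.

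The size is modest. It is a wording error in a subject-safety instruction, softened by discretionary language and by the general rules, and it touches no endpoint, sample size or analysis.

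The conclusion that the direction is wrong follows from the protocol alone. That the intended sign is > and not ≥, and that 2 weeks is the intended cut-off, is inferred from the sibling tables and the printed number, because the algorithms on which the section draws are not reproduced in the protocol.

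**What to change.** In Table 19, Grade 1-2, change the duration on the second line from ≤ 2 weeks to > 2 weeks and keep recurrence as the alternative trigger. Before issuing the change, confirm the sign and the cut-off against the source algorithm cited in Section 6.3.4. Then notify sites, since subjects may continue cetrelimab after the end of study data collection (Section 17.9.1) and the table still governs their care.

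The cost is one symbol and a site notification. No data, analysis or other table needs to change.
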